NHS National Institute for Health Research

NIHR HTA Programme

12 March 2013

The NIHR Evaluation, Trials and Studies Coordinating Centre (NETSCC), based at the University of Southampton, manages evaluation research programmes and activities for the NIHR

PRODIGY: Prevention of long term social disability amongst young people with emerging psychological difficulties: a pilot randomised controlled trial of social recovery cognitive behavioural therapy.

1. Research Objectives

The aim is to undertake a pilot randomised controlled trial involving 50 treatment and 50 control cases to constitute the internal feasibility phase of a substantive trial. The objectives are:

- a) To assess recruitment rate, quality of data collection and follow up.
- b) To provide a final check on procedures in the protocol.
- c) To conduct a qualitative sub-study to inform the objectives, using a qualitative, service user perspective.

At 12 months the trial steering committee will check criteria for progression to a full trial including the data collected in this study as a feasibility phase. The criteria will be:

- a) No necessity for substantive changes to protocol
- b) Recruitment within 80% of planned in the first 12 months.
- c) Retention of participants within the study with baseline and outcome assessments completed over 80% for the secondary outcomes and mediators and 90% for the primary outcome.
- d) Satisfactory delivery of competent and adherent therapy to more than 80% of the treatment group.

If these criteria are met we will continue to recruit and seek approval to extend the study and involve another centre to complete a substantive definitive trial. If these criteria are not met we will continue to collect data up to a total of 100 cases and analyse and report the study as an external pilot.

2. Existing Research

It is now widely recognised that most socially disabling chronic and severe mental health problems begin in adolescence with 75% of all severe and chronic mental illnesses emerging between 15 and 25 (Kessler, et al., 2005; Kim-Cohen, et al., 2003). A series of retrospective studies have consistently shown that severe mental illness is often preceded by social decline, that this often becomes stable, and that such pre-morbid social disability is predictive of the long term course of the disorder (see Fowler, et al., 2010 for review). Between 3% and 5% of adolescents present with complex mental health problems associated with social disability (Kim-Cohen, et al., 2003). The young people at highest risk of long term social disability present with emerging signs of social decline, in association with low level psychotic symptoms, emotional and behavioural disorder (often accompanied by substance misuse problems and risk to self and others) (Kim-Cohen et al., 2003, Kessler et al, 2005). Despite poor outcomes and cost of disorders leading to social decline, young people with complex needs frequently do not access treatment and fewer than 25% of young people and their families who have needs get access to specialist mental health services (DoH, 2008; Singh et al, 2010). More complex cases are found in areas of social disadvantage, and in youth justice, local authority care and learning disability services. The economic costs of not addressing this disability are very large (Mangalore, & Knapp 2007).

Several recent reports have highlighted that there is a major gap in identifying and managing the mental health problems of young people with severe and complex mental health problems and particularly those at risk of social disability (DoH, 2008; Singh et al, 2010). New approaches to detection and intervention are required to meet the needs of these young people. There is a gap in the evidence base for these types of cases. These young people have severe and complex mental health problems and thus they tend not to be suitable or respond to short term evidence based therapies for more discrete mental health problems, such as CBT for anxiety, depression and conduct disorder which are available in IAPT. Also while this group show clear evidence of social disability they do not meet criteria for first episode psychosis and so they are not suitable for first episode psychosis services for which there is now considerable evidence of benefits on social functioning (Addington et al, 2005; Bertelsen, et al., 2008; NICE guidelines schizophrenia, 2009). Our aim in the present project is to identify and target this group and offer a new psychological intervention specifically tailored to their needs.

Current evidence for effective interventions to address social disability amongst young people in the early course of severe mental illness is very limited (see Fowler, et al., 2010 review). A series of studies have been undertaken which have aimed to identify cases at Ultra high risk of poor long term outcome associated with severe mental illness (Addington, et al., 2007; Klosterkotter, et al., 2005; McGorry, et al., 2002; Morrison, et al., 2004; Morrison, et al., 2011; Yung, Phillips, Yuen, & McGorry, 2004; Yung, Stanford, et al., 2006). The

success of the Ultra high risk studies is that it has been shown that it is possible to set up services to identify and treat cohorts of young people who can be identified as having "At Risk Mental States" (ARMS) using defined operational criteria and structured assessment tools (Yung, Phillips, et al., 2006). Furthermore, these studies have consistently identified that those who are at the highest risk are young people who present with social decline as well as sub-threshold psychotic symptoms (Yung, et al., 2010; Lin et al, 2011). However, the focus of these studies has been on prevention of episodes, or symptoms of psychosis, not social disability (Yung, et al., 2010). Recent studies have shown that cohorts identified using these criteria may have more transient problems than previously thought and only a subset go on to have long term social disabiling mental health problems (Yung, et al., 2010; Lin et al, 2011). Several prominent Ultra High Risk researchers are now highlighting an alternative strategy which is to examine functional outcome in the ultra high risk group. This study is consistent with this strategy.

Systematic reviews of CBT for psychosis including nice guidelines have consistently shown moderate effect size on improvements in social disability where this has been assessed as a secondary outcome (Wykes et al, 2008; NICE guidelines for Schizophrenia, 2009), however these studies have predominantly been carried out amongst chronic participants not young people. The feasibility of using CBT with young people who are at ultra high risk of long term poor outcome has been shown the recently completed EDIE 2 mulitcentre study (Morrison, et al., 2011) which has shown reductions in severity of psychotic symptoms. However, the focus of the therapy in EDIE 2 was symptom reduction (French & Morrison, 2004) and this approach neither targeted nor had a significant benefit on social disability. EDIE 2 clearly demonstrated the ability of collaborating sites to recruit young people at high risk and successfully retain them in research and therapy. However, as described above the group recruited in EDIE2 were heterogeneous in terms of social disability. The present trial moves on from EDIE by focussing on a group which have a more homogeneous set of social disability problems defined by low activity levels and targeting this group with a multisystemic intervention which specifically aims to address social disability.

Better outcomes on social disability and hopelessness can be obtained from a more targeted intervention specifically focussed on improving social disability amongst those who have low functioning. We have developed a multisystemic form of CBT which targets social disability and have published a successful MRC trial platform study carried out amongst a group of young people who had established chronic and severe social disability problems some years after first episode psychosis. This trial demonstrated gains in structured activity and hope as well as reductions in symptoms (Fowler, et al., 2009). Clear indications of health economic benefits were also demonstrated (Barton, et al., 2009) although the trial was small and there was a large level of uncertainty associated with these estimates. We have subsequently applied this type of approach in clinical practice widening our selection criteria to include all young people presenting with severe and complex mental health problems at risk of social disability, drawing from our experience with EDIE 2 and this has been highlighted as an example of good practice (Joint Working at the Interface, 2011). We are now ready to undertake the feasibility phase of a substantive trial, which will be the first to specifically aims to address functional disability problems amongst the high risk population.

3. Research Methods

Design: The study will be a single blind, randomised controlled trial comprising of a 9 month intervention and 6 month follow up period involving 50 treatment cases and 50 controls in two centres. The study will constitute the feasibility phase undertaken in preparation for a large multicentre trial. A qualitative sub-study will be embedded within the pilot trial to evaluate the intervention from the subjective perspectives of patients themselves. Depending on data quality and recruitment the data will either be used as an external pilot or as the internal feasibility phase of a substantive trial. The NIHR accredited Norfolk Clinical Trials Unit advised on the development of the protocol and will provide ongoing expertise during the conduct of the study.

Setting: The intervention will be conducted in secondary mental health care settings, by therapists based in outpatient youth mental health early detection and early intervention services in mental health trusts in East Anglia (Norfolk and Suffolk) and Manchester.

Target population: Young people aged between 16-25 presenting with persisting signs of social disability operationally defined as engaged in less than 30 hours structured activity per week and who are presenting to youth services in East Anglia and Manchester. They will also be presenting with either a). Attenuated symptoms of psychosis which meet criteria for an at risk mental state, or b). less severe attenuated psychotic symptoms and the presence of severe and complex mental health problems operationally defined by a score of less than 50 on the Global Assessment of Functioning (GAF) score. All potential referrals will be screened first with GAF

score, then activity levels will be checked by the Time Use Survey and symptoms assessed by the Comprehensive Assessment of At Risk Mental States (CAARMS).

Project timetable: The study will take place over 2.5 years (30 months). This involves a 15 month recruitment period in which we can realistically expect a rate of 3-4 participants randomised per month in each site. Given this rate of recruitment, we can expect to recruit to target to meet the 50 participants required from each site. Each participant will have a 9 month intervention and six month follow up. Recruitment will be monitored continuously via an independent DMEC.

Feasibility of recruitment: We confidently anticipate that we can achieve the recruitment targets by sampling across early detection and youth services in East Anglia and Manchester. Both research sites are nationally recognised centres of clinical excellence which have successfully collaborated and led a series of related studies. The staff and managers involved in both sites are highly motivated to participate and are familiar with recruiting participants into research trials. Both sites have extensive existing links with agencies in primary care, child and adolescent, and adult mental health services, with established referral pathways for recruiting these types of cases into both clinical services and research. Both sites have existing services which already receive referrals of cases with At Risk Mental States at a rate of around 80 per year (total 160 per year in both centres). EDIE 2 data suggests that approximately, 60% of these existing referrals are likely to meet criteria for the present project. Referrals who meet inclusion criteria for existing At Risk Mental State Services will therefore provide approximately 90 suitable cases per year from which to recruit from. In addition, as described above, we will be widening recruitment criteria to include cases who are presenting with early signs of social disability and severe and complex mental health problems but who have less severe attenuated psychotic symptoms (and are thus at present excluded from psychosis and At Risk Mental State Services). Our estimates are that this is likely to at least double the population at risk. Referrals of this type are already received by our existing services (though presently excluded) and further referrals can easily be stimulated via screening and liaison with the close links both services already have with IAPT, counselling and youth offending services. In Norfolk services are being re-oriented to facilitate engagement of young people with severe and complex problems into secondary mental health care. This should facilitate the present study. If recruitment falls 20% below planned rates at key time points we will not proceed to full trial.

Allocation to groups: Following pre trial assessments consenting participants will be randomised to study arms stratified by age (16-19, 20-25); severity of social disability (Not in Education, Employment and Training or not) and meeting symptomatic criteria for an At Risk Mental State or not. Both groups will receive standard treatments as applicable. A remote, randomisation service will assign allocation to groups coordinated by the Norfolk Clinical Trials Unit.

Blinding: We will not be able to blind participants to treatment group. We will blind outcome assessors to group. To do so, following allocation to the treatment or control arm, all participants in the study, their care coordinator and the service user's clinical team will be asked not to reveal the group to which the participants were randomised to their assessor. Interview participants will also be asked at the beginning of each assessment interview not to disclose the group to which the individual was allocated. Outside the assessments, outcome assessors will be shielded from discussion of participants in study forums where the possibility of determining the allocation group of the participants could be determined. Qualitative interviews will be carried out by a researcher from another service or a university researcher independent of the clinical team. With the assistance of the Norfolk CTU we will use a system of web based data entry to ensure that assessors will not have access to information in the data base that would reveal the allocation group. To test the success of blinding we will ask the assessor to guess the allocation group for each participant at the end of each assessment.

Training of trial raters: The trial research assistants will be trained in the use of all measures by members of the team. Joint ratings with one another and with members of the team supervising them will be used to establish reliability.

4. Planned interventions

Experimental: Multisystemic Social Recovery Cognitive Behavioural Therapy (MSRCBT). The intervention used will be an adaptation of the intervention used in our previous studies and described in our therapy manual (Fowler et al, In Press). The therapy is based on a cognitive behavioural model which suggests that social disability evolves as a result of life style patterns of low activity, which are adopted as functional behavioural patterns of avoidance and maintained by lack of hope, sense of agency and low motivation. The intervention involves promoting a sense of agency, hope and motivation and encouraging activity while managing psychotic symptoms and associated problems such as emotional dysfunction and cognitive neuropsychological deficits.

PRODIGY Protocol: Version 4 (18/01/2013)

Preliminary tests of mediation hypotheses provide support for the model (Hodgekins and Fowler, 2010). The focus is pragmatic and combines multisystemic working with use of specific CBT techniques. Therapists adopt assertive outreach youth work principles and also draw from successful social and vocational interventions such as supported education and employment interventions. The intervention specifically focuses on engaging young people with severe and complex mental health problems into treatment and addresses the presence of multiple co-morbidities and potential cognitive difficulties.

The intervention involves three stages: Stage 1 involves assessment and developing a formulation of the person in social recovery. This often involves validation and acceptance of real barriers, threats and difficulties, while focusing on promoting hope for social recovery. Stage 2involves identifying and working towards medium to long term goals guided by a systemic formulation of barriers to recovery. A particularly important aspect of this is identifying specific pathways to meaningful new activities. Where relevant this includes referral to relevant vocational agencies, or alternatively direct liaison with employers or education providers. Cognitive work at this stage involves promoting a sense of agency, consolidating a positive identity and addressing feelings of stigma and negative beliefs about self and others. Stage 3 involves the active promotion of social activity, work, education and leisure linked to meaningful goals, while managing symptoms. This involves specific cognitive behavioural work managing symptoms using behavioural experiments. Treatment fidelity will be assessed by taped treatment sessions and therapy notes using specific assessments of adherence and competence. The procedures are defined in a published treatment manual (Fowler et al In Press) which includes specific case examples. Considerable clinical material and presentation material including video is available for training purposes. The intervention is delivered over 15 sessions over a 9 month therapy window. It is designed for use in secondary early detection and intervention mental health services and differs substantially from currently available short term CBT available in adult mental health, Improving Access to Psychological Therapies (IAPT) and CAMHS services. Therapists will offer a combination of clinic based appointments but also outreach work and home visits to maximise engagement and the application of learning to real life settings. This is a standard approach to delivering CBT with this type of client group. We have already demonstrated the feasibility of delivering this type of approach to young people with severe mental illness in prior feasibility studies and in past trials with similar types of participant groups (e.g. EDIE 2 MRC trial).

Control: Our methodological approach is to compare "current standard outpatient NHS treatment" with our new form of outpatient care "standard NHS treatment plus multisystemic cognitive behaviour therapy". Current existing NHS standard outpatient treatment for young people with non-psychotic severe and complex problems and social disability involves the provision of short term individual and family psychological therapies within the Improving Access to Psychological Therapies (IAPT) and Child and Adolescent Mental Health Services and medication management, support and monitoring. Participants may also receive a range of education, training, vocational and youth work interventions from a variety of statutory and non statutory service providers (including social services, employment and education providers). The aim of the study is to test whether the addition of the provision of multisystemic cognitive behaviour therapy for young people with severe and complex mental health problems and early signs of social disability by secondary mental health care NHS services assists the promotion of social recovery above and beyond that provided by existing interventions available in routine services in the UK. Our intention is to carefully monitor the service contacts received across a range of services in both arms of the trial using a specifically adapted version of Client Service Receipt Inventory (Thornicroft et al, 2006). We will follow procedures adopted in other trials and provide all referrers with a best practice manual for standard treatment which summarises good practice including referral to IAPT services and medication management where appropriate. Participants will not be denied any existing service in either therapy or control arm of the trial. In both arms of the trial they will be encouraged to engage in and continue with existing treatments. In the therapy arm the multisystemic cognitive behaviour therapists are trained to liaise and coordinate their work with other agencies.

We will not be asking referrers to withhold any treatment. We will provide referrers with a best practice manual which gives guidance on providing optimal standard treatment for this type of case. Treatment as usual for this population should involve provision of short term individual and family psychological therapies available in IAPT and Child and Adolescent Mental health services and medication according to disorder specific protocols. Standard psychiatric care, psychological and vocational interventions from a variety of agencies will also be available to both treatment and control arms. All service contacts will be monitored during the trial duration. In addition our assessments will identify any risks to self or others and this will be communicated to the referring clinicians.

Anticipated problems with compliance: We are aware that young people with severe and complex mental health problems who are socially withdrawn with low activity levels often present challenges to clinical services, not least, that they may disengage from treatment. Despite this, our clinical experience with this type of

patient group is good. In our trial platform we achieved follow up data from over 90% of eligible clients on constructive economic activity (work, education) assessed by telephone and over 80 % from face to face interview assessments and we are confident in achieving similar levels of outcome with this participant group. Importantly the primary outcome assessment is Time Use and a useful estimate of time in constructive economic activity (work, education, voluntary work) can be assessed by telephone contact and triangulated by case worker report. All who enter the trial will have given permission to be contacted in this way. Similarly both our intervention and our assessment procedures are designed to be flexible and work in an outreach way to deliver the intervention and conduct assessments wherever is suitable for the participant. We have developed extensive experience over many years in managing such procedures in ways which are welcomed by young people with severe and complex mental health problems, safe for assessors and therapists and result in good levels of outcome.

Training and delivery

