8. Statistical analysis of outcome: The main aim of the pilot project is to undertake feasibility studies. The criteria for the first phase are therefore the ability to successfully recruit a sample of suitable cases. Analysis of baseline data of the first phase aims to describe the mean and SD of the primary and secondary outcome measures to prepare a definitive sample size calculation.

If it is decided to set aside the results and publish them as an external pilot, the main analyses will use general linear models with the inclusion of treatment group and stratification baseline variables. The outcome variables will be checked for distributional assumptions (i.e. following a Normal distribution) and transformation will be applied if necessary,

For both the primary and secondary outcomes we will check the extent and patterns of missing data and use multiple imputation if it is felt necessary. Factors to include in the imputation model will be those that are likely to be related to the outcomes (a clinical decision) and those related to missingness (a statistical decision). The analysis using imputed data will be a secondary, sensitivity, analysis with complete case analysis being the primary analysis.

9. Economic evaluation: The estimation of cost-effectiveness, within a health technology assessment, is an iterative process (Ramsey et al, 2001). Here we aim to monitor levels of resource use and quality of life, with a view to inform the decision as to how costs and benefits would be measured as part of any future more definitive study. A preliminary within trial cost-effectiveness analysis of multisystemic social recovery CBT compared to treatment as usual will also be undertaken. In line with guidance by the National Institute of Health and Clinical Excellence (NICE, 2008) costs will be calculated from the perspective of the NHS and personal social services (PSS). A modified version of the Client Service Receipt Inventory (Thornicroft et al, 2006) will be used to monitor levels of resource use associated with both interventions (including intervention staff training and supervision, along with all visit related costs) and other NHS and PSS resource items, such as hospital admissions/visits, which may relate to the interventions in question. Appropriate unit costs (e.g. Curtis et al, 2009) will subsequently be attached to all items of resource use.

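### Centre is named neither among the allocation factors nor in the analysis model, although two locally staffed sites each recruit 50

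*Protocol*

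**What the plan says.** Protocol section 3, Allocation to groups, lists three factors. Participants are "randomised to study arms stratified by age (16-19, 20-25); severity of social disability" (NEET or not) and, as the third factor, by "meeting symptomatic criteria for an At Risk Mental State or not". The mechanism is described in one sentence: "A remote, randomisation service will assign allocation to groups coordinated by the Norfolk Clinical Trials Unit". The protocol nowhere says that allocation is blocked, minimised or otherwise balanced by centre.

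The same section describes a trial "involving 50 treatment cases and 50 controls in two centres", and its timetable paragraph states that "we can expect to recruit to target to meet the 50 participants required from each site".

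Section 8 gives the main analysis for the case where the results are reported as an external pilot: "general linear models with the inclusion of treatment group and stratification baseline variables". Centre is not named there either.

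**The concern.** Centre divides this sample in half, and several features of the trial are organised by centre. The Setting paragraph bases the therapists in the youth services of the trusts in each area. Under Feasibility of recruitment, each site has its own existing services and referral routes, and a service re-orientation is reported for Norfolk only. Section 13 has senior research assistants recruited in each centre. The comparator is whatever standard provision participants receive, and the primary outcome is hours of work, education and other structured activity. Either could plausibly vary with locality.

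If allocation is not balanced within centre, the arms can by chance end up with different shares of the two centres. Any difference in mean activity between centres then enters the treatment comparison, unless the model adjusts for centre. The three listed factors do not prevent this, and a model that follows the list does not remove it.

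**Working it through.** **Inputs from the protocol**
- Two centres, 50 per arm and 50 per site (section 3).
- Recruitment of 3 to 4 per month per site for 15 months (section 3, Project timetable).
- Minimum clinically significant benefit 4 hours; SD about 9 hours (section 7).

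**Assumptions, not in the protocol**
- Exactly 50 recruited at each site.
- Permuted blocks of 4 for the simulations.
- A difference of 2 to 8 hours in mean activity between centres.

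**1. The plan's own figure.** 15 × 3 = 45 and 15 × 4 = 60 per site, so 50 per site lies within the stated rate. 2 × 50 = 100 = 50 + 50. The site target is consistent with the arm sizes.

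**2. Chance imbalance without centre, exact.** With 100 participants, 50 treated and 50 at a given site, the number treated at that site follows a hypergeometric distribution (100, 50, 50). Its mean is 25 and its SD is √(50 × 0.5 × 0.5 × 50/99) = 2.51. The two-sided probabilities are:

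| Split within a site | Probability |
|---|---|
| 28:22 or worse | 0.317 |
| 30:20 or worse | 0.071 |
| 32:18 or worse | 0.009 |

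**3. Chance imbalance with stratified blocks, simulated.** The listed factors give 2 × 2 × 2 = 8 strata. Adding centre gives 16 cells, averaging 100/16 = 6.25 people. There were 8,000 allocations per scheme, with equally likely strata.

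| | 8 strata, no centre | 16 cells, with centre |
|---|---|---|
| 30:20 or worse in a given site | 8.0% | 0.04% |
| 28:22 or worse in a given site | 32.9% | 4.5% |
| 95% range of treated cases in a site of 50 | 20 to 30 | 23 to 27 |

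Stratifying by the three patient factors therefore gives almost no protection against imbalance by centre: 8.0% is close to the exact 7.1%.

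**4. Cost in overall balance.** In a second simulation with assumed factor prevalences of 0.5, 0.5 and 0.6, the chance of an overall arm difference of 10 or more rose from under 0.1% to 1.2% when 16 blocked cells replaced 8.

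**5. Effect on an unadjusted estimate.** Shift = (difference between arms in the share from one centre) × (difference between centres in mean hours). For 30:20 at one site and 20:30 at the other, the shares are 30/50 and 20/50, a difference of 0.20.
- Centres 2 hours apart: 0.20 × 2 = 0.4 hours, or 10% of the 4-hour benefit.
- Centres 8 hours apart: 0.20 × 8 = 1.6 hours, or 40% of it.

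**6. Comparison with sampling error.** Standard error of the arm difference = 9 × √(2/50) = 1.8 hours. The shift is 0.4/1.8 = 0.22 to 1.6/1.8 = 0.89 standard errors.

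**The case against.** The case against giving this much weight is substantial, and most of it stands.

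- Randomisation is valid without stratifying by centre. A lopsided site is chance error and not systematic bias, and more than nine trials in ten would have no split as bad as 30:20 at a given site.
- Even at the top of the assumed range, the shift stays below one standard error. Eight hours is itself nearly one SD of the outcome.
- The protocol gives no difference between centres in usual care or in activity. It also takes steps that would narrow any such difference: a best-practice manual for referrers, joint ratings between assessors, and a manualised therapy with common training and supervision.
- Section 8 says which variables are included; it does not say that no others may be. A statistical analysis plan or the trials unit's randomisation specification, neither of which is shown, could name centre.
- This is a feasibility pilot, and none of the progression criteria in section 1 turns on the treatment effect.

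What remains is narrow. The protocol does set out its allocation factors and leaves centre off that list, and the only model it describes is tied to the list.

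Two further consequences might be inferred, and the document supports neither. One is that centres added later would inherit the scheme. Appendix a names two extra centres (section 1 speaks of one) and requires a separate full-trial application, where centre could be added. The other is that uneven allocation would overload one site's therapists and threaten the therapy-delivery criterion. That criterion applies to the treatment group as a whole, and no therapist numbers or capacity are given.

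**Conclusion.** The point holds as a modest, inexpensive improvement. Centre is named in neither the allocation factors nor the section 8 model, although it splits the sample into two locally run halves. The chance of a 30:20 or worse split at a given site is about 7% (exact) to 8% (simulated), and under 0.1% with centre added in blocked cells. Such a split would move an unadjusted estimate by 0.4 to 1.6 hours, and only if the centres differ by 2 to 8 hours. That difference is assumed, as are the block size and exactly 50 per site.

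A reader might go further and conclude that the comparison is biased, that the two centres are known to differ in usual care, or that the analysis excludes centre. The text supports none of these. Adjusting for centre in the model would by itself remove most of the shift.

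**What to change.** Add centre to the factors listed under Allocation to groups in section 3, and name centre as a covariate in the section 8 model. If the trials unit's specification already balances by centre, only the protocol text needs correcting to match.

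The cost is a set-up change in the remote randomisation service and a short amendment. Sample size and participant burden do not change. With permuted blocks there would be 16 cells averaging about 6 people, and overall balance would be slightly worse (step 4 of the working). Minimisation with a random element is an option that avoids small cells, but the figures above are for blocked cells and were not run for minimisation. The covariate costs one degree of freedom: with complete data on 100 participants, an intercept, treatment and three binary factors leave 95, and adding centre leaves 94.
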